In conducting this phase 1 study, we will utilize the multidisciplinary collaboration of an experienced group of scientists, surgeons and physical therapists in a unique environment at the University of Pittsburgh and the USAISR (United States Army Institute of Surgical Research) at Brooke Army Medical Center (BAMC) San Antonio, Texas. The main outcome measures will be to (a) quantify the length and volume of fibrosis in the injured hamstring muscle, based on a baseline 3 Tesla MRI and a subsequent follow-up MRI examination 6 months post-injury and (b) prospectively follow the subjects to evaluate the amount of scarring and time to return to prior activity. Safety and tolerability will be assessed by monitoring adverse events, symptoms (dizziness, new fatigue, peripheral edema or urinary symptoms), hypotension, and laboratory measures of liver and renal function, hemoglobin and hematocrit counts and serum potassium and uric acid levels.

A 1999 study in the United Kingdom^67 examined the safety of losartan potassium post-marketing in over 14,000 patients. The results of this study indicate losartan potassium, like other angiotensin II receptor antagonists (ARBs), does not present any significant adverse events. The most commonly cited specific adverse events include dizziness, headache, malaise, nausea, lassitude, cough, diarrhea, dyspnea and impotence. A literature review conducted by Sica *et al.* found other adverse events being decreases in hemoglobin and hematocrit counts, dysgeusia and ageusia, migraines and acute psychosis, hepatic abnormalities, angioedema, increase in serum potassium, decrease in serum uric acid, and changes in renal function. As is the case with all drugs directly affecting the renin-angiotensin system, Losartan should not be taken by anyone who is pregnant or thinks they may be pregnant. The use of these drugs can cause neonatal injury, hypotension, neonatal skull hypoplasia, anuria, renal failure and death. To our knowledge losartan potassium has not been withdrawn from research or marketing in the United States or any other country.

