#### **4.2 Subject exclusion criteria**

Subjects will be excluded if they: 1) have had a previous hamstring injury on the same side or chronic symptoms; 2) have an injury that requires surgical intervention (e.g. avulsion with associated bony involvement, grade III complete tears); 3) have concurrent lower back symptoms; 4) are pregnant or breast feeding; 5) are a smoker; 6) have contraindications to Losartan therapy (e.g. known hypersensitivity to losartan, hepatic impairment); 7) currently use angiotensin I converting enzyme inhibitor (ACEI) / angiotensin II receptor blocker (ARB); 8) have hypertension (blood pressure greater than or equal to 140 mm Hg systolic pressure or greater than or equal to 90 mm Hg diastolic pressure); 9) have hypotension (blood pressure less than or equal to 90 mm Hg systolic pressure or less than or equal to 60 mm disastolic pressure); 10) have orthostatic hypotension defined as a drop in systolic pressure greater than or equal to 20 mm Hg or a drop in diastolic blood pressure greater than or equal to 10 mm Hg or reports of lightheadedness or dizziness would be considered abnormal upon standing or 11) have diabetes mellitus, cardio-vascular, renal or hepatic co-morbidities.

Additionally, because participation in this study requires undergoing MRI, subjects will be excluded if they: 1) had prior surgery for an aneurysm; 2) have a cardiac pacemaker; 3) have metal fragments in the eyes, brain or

spinal cord from shrapnel, metal work or welding; 4) have surgical implants, such as an ear implant or neurostimulator; 5) have a history of claustrophobia or 6) have a history of not tolerating previous MRI scans without medication.

For the military personnel, individuals recruited to participate in this study should not have a scheduled deployment within 6 months following initial injury to ensure adequate follow up.

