### 6.3.2 Baseline Assessment of Injury

At the time of study enrollment, the subject will be interviewed about the mechanism of injury (movement that was made during injury), presence or absence previous symptoms at the injury site, presence or absence of ecchymosis and the ability to walk and run. An examination will include inspection to confirm the presence or absence of ecchymosis. Palpation of the posterior thigh will be performed with the subject in prone and the knee extended. The point of greatest pain will be marked and the distance to the ischial tuberosity will be measured and the presence or absence of a palpable defect will be recorded. Pain during resisted knee flexion will be graded on an 11 point (0 to 10) numerical pain rating scale.

Subjects will be eligible for participation in the study if the physical examination reveals: 1) localized tenderness with or without a palpable defect; 2) pain and weakness with resisted knee flexion with the individual in the prone position and 3) pain and a limitation (in comparison to the contralateral leg) in the popliteal angle with the hip at 90 degrees of flexion. Presence of a grade II/III hamstring strain will be confirmed on the baseline MRI that is performed prior to randomization. MRI evidence of a grade II/III hamstring strain includes edema with architectural disruption indicating a partial tear (grade II) or edema with complete rupture of the muscle or tendon (grade III). Excellent intra- and inter-rater reliability has been reported for this MRI grading system of acute hamstring injuries.

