**Table 4 – Summary of MRI Parameters**

Sequence	Slice/Gap Thickness (mm)	Matrix	Field of View
Axial T1 a	8/1	512 x 180	40 cm/phase 75
Sagittal T1 a	5/2	194 x 384	38 cm/phase 84
Coronal T1 a	5/2	192 x 512	40 cm/phase 75
Axial STIR b	8/1	256 x 256	40 cm/phase 75
Axial T2 FS c	8/1	203 x 384	40 cm/phase 75
Sagittal T2 FS c	5/2	194 x 384	38 cm/phase 84
Coronal STIR b	5/2	256 x 256	40 cm/phase 75

a T1 weighted non-fat saturated.  
b Short inversion recovery time.  
c T2 weighted fat saturated.

The primary MRI outcome measures for analysis will be the maximal crano-caudal length and volume of the injury/scar tissue. To calculate volume of injury/scar tissue, the area of injury/scar tissue will be determined on each slice. This area will be multiplied by the slice thickness and summed across all slices in which the injury/scar tissue is visible. Additionally, total volume of the involved compared to the non-involved hamstring muscles will be determined as a measure of muscle atrophy.

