#### **Specific Aim #2: Recovery of Hamstring Muscle Function and Structure.**

Recovery of muscle function will be assessed in terms of hamstring flexibility and strength. Hamstring length will be assessed by measuring the popliteal angle as described by ten Berge et al. To account for variability between subjects, hamstring flexibility will be expressed as the difference in popliteal angle between the hamstring-injured and contra-lateral normal leg. To assess hamstring strength, isometric testing with the knee flexed to 30° and 90° will be performed before treatment and at 1, 2, 3, 4 and 6 weeks and 6 months after enrolment and isokinetic testing at 60° and 180°/sec will be performed 6 weeks and 6 months after enrolment. The detailed procedures for measuring hamstring flexibility and strength are described in section 6.4.2.2.

3 Tesla MRI will be performed at enrolment and at 6 months follow-up to assess hamstring structure in terms of the length and volume of the injury and scarring. Additionally total volume of the injured and contra-lateral hamstrings will be calculated to determine the degree of atrophy. The detailed procedures for use of 3T MRI to assess hamstring structure are described in section 6.4.2.3.

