**Specific Aim #2: Recovery of Hamstring Muscle Function and Structure**

The primary endpoints to assess hamstring muscle function are the injured to contra-lateral leg differences in the popliteal angle at 6 weeks and 6 months and the injured to contra-lateral ratio of peak isokinetic hamstring torque at 6 weeks and 6 months.

The primary endpoint to assess hamstring structure will be the length and volume of fibrosis within the hamstrings at 6 months as evidence on 3 Tesla MRI.

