## **9.4        Effectiveness analysis**

The distribution of baseline characteristics and important prognostic factors (age, sex, body mass index, pre-injury activity level, etc) will be summarized overall, and by treatment (versus control) group to assess the effectiveness of the randomized allocation. Continuous variables will be summarized with means and standard deviations, and medians and inter-quartile ranges. Categorical data will be summarized using frequencies and percentages. We will then graphically explore the distributions of the primary outcome variables (for normality or skewedness and potential outliers) using q-q plots and histograms before conducting any tests to compare the two groups. When appropriate, transformations will be applied to outcome measures that are not normally distributed.

We anticipate minimal loss to follow-up (<5% of patients) at the 6 month assessment and only 10-15% loss to follow-up at 12 months post-injury. The primary outcome measures (safety and tolerance, recovery of muscle structure and function, return to prior level of function) will be evaluated between 6 weeks and 6 months; therefore the only outcome that could appreciably be affected by lost to follow-up is recurrence of injury within 12 months. We will compare baseline characteristics between participants and drop-outs, obtain reasons for

study drop (to investigate the possible missing data mechanism), and will also conduct a sensitivity analysis (assigning poor scores and good scores to those persons with missing information differentially by treatment assignment) to evaluate the impact on our study results.

For outcome variables that are measured repeatedly, we will use mixed models to adjust for correlation among the observations from the same person as well as a clustering effect for each site. In these models, subject characteristics such as age, sex, and treatment group will be fixed effect predictors, and subject and site identification will be included as random effects. Depending on the type of outcome variable of interest, we will employ linear mixed models or mixed effect logistic regression. Though we do not anticipate statistically significant differences between the Losartan and placebo groups due to the small sample size, these analyses will guide us in developing future clinical trials.

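### The plan compares absolute 6-month scar length and volume between arms and does not say how the lesion size measured on the pre-treatment MRI enters the analysis

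*Combined protocol and SAP*

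**What the plan says.** Section 9.1.1, Specific Aim #2, sets the structural endpoint: "The primary endpoint to assess hamstring structure will be the length and volume of fibrosis within the hamstrings at 6 months". Section 6.4.2.3 describes the measurement in the same absolute terms: "The primary MRI outcome measures for analysis will be the maximal crano-caudal length and volume of the injury/scar tissue". For volume, the lesion area is found on each slice, and then "This area will be multiplied by the slice thickness and summed across all slices in which the injury/scar tissue is visible". Neither definition contains a ratio to baseline, a change score or a baseline adjustment.

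The baseline measurement is already planned. Section 7.2 (Effectiveness assessments) has MRI at enrolment and at 6 months "to assess hamstring structure in terms of the length and volume of the injury and scarring". Section 1.2 goes furthest in linking the two scans. It says that fibrosis will be quantified "based on a baseline 3 Tesla MRI and a subsequent follow-up MRI examination 6 months post-injury", without saying how the first scan contributes.

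On analysis, section 9.4 says of repeatedly measured outcomes that "subject characteristics such as age, sex, and treatment group will be fixed effect predictors", with subject and site as random effects. Its list of prognostic factors to be summarised names age, sex, body mass index and pre-injury activity, and leaves the rest open. Section 3.2 describes 1:1 allocation in random blocks of two and four and mentions no stratification factor.

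On severity at entry, section 6.3.2 defines the eligible MRI findings as "edema with architectural disruption indicating a partial tear (grade II) or edema with complete rupture of the muscle or tendon (grade III"). Section 4.2 excludes subjects who "have an injury that requires surgical intervention (e.g. avulsion with associated bony involvement, grade III complete tears").

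**The concern.** Subjects enter with lesions of different sizes, and the amount of scar at 6 months may depend in part on the size of the initial lesion. If it does, a chance difference in initial lesion size between two arms of 10 carries over, in proportion to r, into the fibrosis comparison. It also stays in the between-subject SD that the pilot reports.

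This matters because sections 2.1 and 9.2 disclaim power and name effect size and variability as what the efficacy part is to deliver for a later trial. Precision of the estimate is therefore what the structural endpoint is for.

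The plan's other efficacy measures already deal with between-subject variation. Flexibility, peak torque and atrophy are each expressed relative to the other leg. Scar cannot be handled that way, because the uninjured leg has none. The baseline lesion is the within-subject reference that the plan already collects.

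**Working it through.** **Plan's own figure.** Section 9.2 gives 20 patients, 10 per group, as an approved number. It states no alpha, power, effect size or SD, so there is nothing to reproduce.

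**Inputs.** From the documents: n = 10 per arm, 1:1 allocation, no stated stratification. Assumed: two-sided 95% intervals, equal SDs in the two arms, approximate normality, and r between 0.2 and 0.7. All results are in SD units.

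**Chance imbalance in baseline lesion size.**
- SE of the difference in means = √(2/10) = 0.447 SD.
- P(|difference| > 0.5 SD) = 2 × [1 − Φ(0.5/0.447)] = 0.26.
- P(|difference| > 0.75 SD) = 0.09.

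**Carry-over.** A 0.5 SD imbalance shifts the unadjusted 6-month difference by r × 0.5 SD: 0.15 at r = 0.3, 0.20 at 0.4, 0.30 at 0.6 and 0.35 at 0.7.

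**Precision, unadjusted.** Half-width = t(18 df) × √(2/10) = 2.101 × 0.447 = 0.94 SD.

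**Precision, adjusted for one baseline covariate.** Half-width = t(17 df) × √(2/10) × √(1 + 1/(2n − 4)) × √(1 − r²) = 2.110 × 0.447 × √(1 + 1/16) × √(1 − r²) = 0.973 × √(1 − r²).

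| Assumed r | Shift from a 0.5 SD imbalance | Adjusted half-width (unadjusted 0.94) | Later trial, N per arm for a 0.5 SD effect (unadjusted 63) |
|---|---|---|---|
| 0.2 | 0.10 | 0.95 | 61 |
| 0.3 | 0.15 | 0.93 | 58 |
| 0.4 | 0.20 | 0.89 | 53 |
| 0.6 | 0.30 | 0.78 | 41 |
| 0.7 | 0.35 | 0.69 | 33 |

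The last column uses N = 2 × (1.96 + 0.84)² × (1 − r²)/0.5², that is 80% power, two-sided 5%, normal approximation, rounded up. It applies only if the later trial also adjusts.

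These half-widths use the true SD. Averaged over simulated trials, where the SD is estimated, they run 0.01 to 0.02 lower: about 0.93 unadjusted, against about 0.91, 0.88, 0.77 and 0.68 at r = 0.3, 0.4, 0.6 and 0.7. The pattern is the same.

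**Break-even.** Adjustment helps when 0.973 × √(1 − r²) < 0.940, so r² > 1 − (0.940/0.973)² ≈ 0.067, or r above about 0.26.

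**Why not a change score.** With equal SDs its variance is 2(1 − r) times that of the 6-month value, which is worse than no adjustment when r < 0.5. It would also subtract one tissue state from another: by section 6.3.2 the acute scan shows edema and disruption, whereas the 6-month target is fibrosis.

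**The case against.** The strongest reply is that the plan does not shut the baseline scan out. Section 1.2 refers to it, the covariate list in section 9.4 is open, and MRI is done twice, so it could fall under the mixed models for repeated outcomes. This stands in part, and a reader who infers that the plan ignores the baseline MRI goes too far. But no baseline term is written down, and section 9.1.1 names 6 months only. Treating the two scans as one repeated outcome would pool acute lesion with scar. An open list permits the adjustment but leaves the choice until after the data are seen.

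Second, the gain depends on r, which the documents do not give. This stands. A reader might infer that scar size is largely fixed before the first dose; no section supports that, and the difference in tissue between the two scans argues against taking a high r for granted. The severity range is also narrower than section 6.3.2 alone suggests, because section 4.2 excludes surgical injuries and gives complete grade III tears as an example. The two sections leave unclear how much of grade III remains. A narrower range would probably lower r.

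Third, randomization protects the comparison, and sections 9.2 and 9.4 expect no significant differences. This also stands: it would be wrong to call the unadjusted estimate biased. The shifts of 0.15 to 0.35 SD lie well inside a half-width of 0.94 SD, and the unadjusted SD is the right input for a later trial that does not adjust.

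Fourth, the scans are kept, so an adjusted estimate could be computed afterwards. True, but an adjustment chosen after the data are seen carries less weight than one fixed in advance.

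A reader might want to extend the point to the functional endpoints. The documents do not support that. Popliteal angle is measured repeatedly from baseline and already falls under the section 9.4 models. Isokinetic torque has no baseline test, and nothing shows that acute isometric strength, measured when resisted knee flexion is painful, could stand in for it.

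**Conclusion.** The point holds as one of precision and prespecification. The plan measures lesion length and volume before treatment but does not say how they enter the comparison of 6-month scar. At 10 per arm, an imbalance above 0.5 SD arises by chance in about 26% of randomizations. What adjustment is worth turns on an unknown r: very little at 0.3, a half-width about 5% shorter at 0.4 (0.89 against 0.94), about 17% shorter at 0.6 and about 26% shorter at 0.7, with a slight loss below about 0.26. These figures assume normality and a single covariate; the age, sex and site terms in section 9.4 would take further degrees of freedom. The change is worth making because it is nearly free and because the pilot would then report r itself, which the next trial needs for its sample size.

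**What to change.** In section 9.1.1, keep 6-month scar length and volume as the structural endpoint, and state that the acute lesion is not subtracted as though it were fibrosis.

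In section 9.4, add that each measure will be compared between arms with its own baseline MRI counterpart as covariate (length for length, volume for volume), on the log scale if skewed. Report adjusted and unadjusted estimates with confidence intervals, the residual SD, and the observed correlation between baseline lesion and 6-month scar.

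Cost: wording in two sections and one degree of freedom per model. No new scans or visits are needed, because length and volume on the enrolment scan are already planned. The downside is a trivial loss of precision if the correlation proves weak, which the side-by-side estimates would show.

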#### **Specific Aim #3: Time to Return to Prior Level of Function**

The primary outcome for return to sports will be the number of days from injury to full, unrestricted return to practice.

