#### **Specific Aim #3: To determine the effect of Losartan on time to return to prior level of function following an acute grade II or III hamstring strain.**

*Hypothesis 3:* Subjects who receive Losartan for a short duration along with the current standard of care treatment after sustaining an acute grade II or III

hamstring muscle injury will have a faster return to their prior level of sports activity when compared to the control group who receives the current standard of care treatment without Losartan.

**Specific Aim #4: To determine the effect of losartan on recurrence of injury following an acute grade II or III hamstring strain.**

*Hypothesis 4:* Subjects who receive Losartan will have a lower incidence of recurrent injury after return to their prior level of sports and military activity compared to the control group who receives the current standard of care treatment without Losartan.

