### **3. Study Design:**

We will conduct a **phase 1 prospective double-blind placebo-controlled randomized clinical trial** to evaluate the safety and tolerability and to provide preliminary data related to the the magnitude and variability of the effect of Losartan, an angiotensin II receptor blocker, for the treatment of acute grade II and III hamstring strains in athletes and military personnel. Safety will be evaluated in terms of the adverse event profile and tolerability (Specific Aim 1). The effect of Losartan will be evaluated in terms of function and structure of the muscle (Specific Aim 2), time to return to sports (Specific Aim 3), and recurrence of injury (Specific Aim 4). Subjects will be followed over the course of 12 months after injury.

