**Figure 1 – Flow Chart for Study Design**

### **3.2 Allocation to treatment**

Subjects will be randomized in a 1:1 ratio to either treatment with Losartan or placebo. Both groups will otherwise undergo the same standard of care rehabilitation for treatment of an acute hamstring injury. The randomization list will be generated using a random number generator. An equal number of subjects will be allocated to each group in random block sizes of two and four. Group assignments will be placed in sequentially numbered opaque envelopes, which will be opened by the Project Coordinator at each site once the participant has agreed to participate in the study and baseline testing has been completed to confirm subject eligibility. Thus the treatment allocation will be concealed from the Project Coordinator and others responsible for recruitment. To minimize bias throughout the study, both the subject and individuals responsible for outcome measure collection/analysis will remain blinded to the group assignment.

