## **9.2        Sample size determination**

With an approved sample size of 20 patients (10 in each group), we will not have enough statistical power to detect statistically significant differences in clinical measures between the Losartan and placebo groups. Therefore the objective of this phase 1 trial is to observe trends by group and estimate effect sizes that can be used to inform power calculations in future clinical trials.

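### Section 9.4 gives no time-to-event analysis and no non-return rule for days to return to sport, so subjects without a return date would fall out of the Aim 3 comparison

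*Combined protocol and SAP*

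**What the plan says.** The Aim 3 hypothesis in section 2.1 is that losartan subjects "will have a faster return to their prior level of sports activity when compared to the control group". Section 9.1.1 sets the endpoint: "The primary outcome for return to sports will be the number of days from injury to full, unrestricted return to practice". Section 7.2 repeats it, and section 6.4.2.1 adds military training to practice. None of these gives a cut-off date or says what is recorded for a subject who does not return.

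Section 9.4 covers analysis.
- The primary outcome variables are plotted and checked for skewness before any group tests, and "When appropriate, transformations will be applied to outcome measures that are not normally distributed".
- Mixed models are for outcomes measured repeatedly.
- Logistic regression, and Cox regression if the data allow, are for recurrence (Aim 4).
- Expected loss is under 5% at 6 months and 10 to 15% at 12 months. The main outcomes, including return to prior function, are evaluated between 6 weeks and 6 months, and "therefore the only outcome that could appreciably be affected by lost to follow-up is recurrence of injury within 12 months".
- Drop-outs are compared with participants at baseline, and a sensitivity analysis gives poor and good scores to subjects with missing data, differently by arm.

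Sections 5.1.1, 8.4 and 13.1 withdraw subjects for low adherence, symptomatic hypotension, abnormal laboratory values or pregnancy, and replace them. Section 8.4 ends study visits after withdrawal for an adverse event. Section 13.1 says no research data are collected after withdrawal. Section 3 states: "Subjects will be followed over the course of 12 months after injury".

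**The concern.** Faster return is a question about time to an event, and some subjects may not have had the event when observation stops. Checks of normality, transformations and comparisons of means use only subjects with a return date. The comparison would then be conditional on having returned while under observation, which omits the slowest healers and anyone withdrawn before return.

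The stated purpose is to "observe trends by group and estimate effect sizes that can be used to inform power calculations in future clinical trials". If the proportion without a return date differs by arm, the effect size passed to the next trial is wrong, and nothing in the planned output would show it.

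**Working it through.** **1. What the plan's own figures give.** The sample size is 10 + 10 = 20. The documents give no expected return time, SD, effect or non-return rate for Aim 3, so there is no Aim 3 figure to reproduce. The expected losses are under 0.05 × 20 = 1 subject at 6 months and 0.10 to 0.15 × 20 = 2 to 3 subjects at 12 months.

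**2. Does the loss-to-follow-up statement hold?** Study drug starts within 7 days of injury and runs 4 weeks, so dosing ends by about day 7 + 28 = 35. Blood is drawn up to 6 weeks after randomization. Withdrawals for adherence, hypotension or laboratory values would mostly fall in that period. The two earlier cases in section 1.2 regained flexibility and strength 6 to 9 weeks after injury (42 to 63 days). That is only two patients, and it is not the same as full return, but it suggests that withdrawal can come before return. The figure of under 5% also describes subjects who are lost. It does not describe subjects who attend every visit and never meet the return criteria in section 6.4.1, which include a 40-yard sprint without tightness.

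**3. How likely is at least one such subject?** If a fraction p of subjects has no observed return (assumed), P(at least one of 20) = 1 − (1 − p)^20.
- p = 5%: 64%
- p = 10%: 88%
- p = 15%: 96%

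**4. Effect on the estimate.** Assumed inputs: lognormal return times among returners, medians 42 days (placebo) and 32 days (losartan), log-SD 0.5.

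Mean among returners = median × exp(0.5²/2).
- Placebo: 42 × 1.133 = 47.6
- Losartan: 32 × 1.133 = 36.3
- Complete-case difference: about 11.3 days

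The restricted mean to 180 days, with a fraction p followed to 180 days without returning, is (1 − p) × m + p × 180. Here m is the returners' mean capped at 180 days: 47.5 and 36.3.

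| Non-return, placebo v losartan | Placebo | Losartan | Difference (days) |
|---|---|---|---|
| 5% v 5% | 54.2 | 43.4 | 10.7 |
| 10% v 10% | 60.8 | 50.6 | 10.2 |
| 20% v 20% | 74.0 | 65.0 | 9.0 |
| 5% v 0% | 54.2 | 36.3 | 17.9 |
| 20% v 10% | 74.0 | 50.6 | 23.4 |
| 0% v 5% | 47.5 | 43.4 | 4.1 |

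Equal non-return moves the estimate by about 1 to 2 days from the complete-case value. Unequal non-return moves it by about 7 to 12 days in these examples, in either direction. The complete-case expectation stays near 11 days in every row, so it cannot register the difference.

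**5. The undefined sensitivity score.** If the poor value is 365 rather than 180 days, one subject moves a 10-subject arm mean by (365 − 180)/10 = 18.5 days. That is more than the assumed complete-case difference.

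**The case against.** The trial is small and says so: "With an approved sample size of 20 patients (10 in each group), we will not have enough statistical power to detect statistically significant differences". Safety is Aim 1. Expected loss at 6 months is under one subject. Subjects with previous same-side injury, chronic symptoms or an injury needing surgery are excluded, so non-return may be rare. The plan also includes a drop-out comparison and a poor/good-score sensitivity analysis, which is a partial safeguard. With equal non-return the bias is only 1 to 2 days. These points stand, and they limit the size of the problem. They do not remove it, because estimating an effect size is the trial's stated purpose and the sensitivity analysis has no day values.

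Two stronger readings are tempting. A reader might infer that the plan treats days to return as a complete continuous variable. It never says so. Section 9.4 names no Aim 3 method, and that reading is drawn from the general text. A reader might also infer that a subject re-injured before return has no value. The count runs from injury to full return, so a setback lengthens it, and a value exists if the subject later returns during follow-up.

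A time-to-event analysis does not by itself solve early withdrawal. Censoring at withdrawal assumes that withdrawal is unrelated to prognosis, which may be untrue for reasons linked to the drug.

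**Conclusion.** The point holds as an omission joined to an unsupported rationale. Section 9.4 gives no time-to-event analysis, censoring rule or non-return rule for an endpoint that needs them, and its claim that only recurrence is exposed to loss does not follow from the protocol's own withdrawal rules. It should be corrected, although the trial can be run without it.

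The bias is small if non-return and withdrawal are balanced (about 9 to 11 days against a complete-case 11). It is material if they are not (about 18 days with 5% v 0%, about 23 with 20% v 10%). These figures rest on assumed medians, spread and non-return rates, and they treat non-returners as followed to 180 days. A reader might infer that a large bias is to be expected. The documents do not support that, because they give no non-return rate and no sign that the arms will differ in it.

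**What to change.** In section 9.4:
- Analyse days to return as time-to-event in all randomised subjects. Report Kaplan-Meier curves and a median or restricted mean difference to 6 months with a 95% CI, with log-rank or Cox as support.
- Censor at last contact or at the end of follow-up. Let the clock run through a re-injury before return.
- Delete or correct the statement that only recurrence could be appreciably affected by loss to follow-up.
- Define in days the poor and good values for the sensitivity analysis.
- State that censoring at withdrawal may be informative.

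In data collection, confirm or add a date-of-full-return field. Table 1 schedules activity level at every follow-up contact, but the CRF content listed in section 11.1 shows no return-date item, so it cannot be assumed that the date is already captured. Where possible, collect this date after study drug is stopped, in line with the intent-to-treat statement in section 9.3. Section 13.1 would have to be reconciled with that.

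The cost is SAP wording, possibly one CRF field, and a less precise estimate than one from returners alone. No extra subjects or visits are needed.
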